4.2.5 Supplementary Analyses for Primary Endpoint(s)

In addition to the primary analysis for each efficacy score at Week 24, the same analysis will be performed for each other clinical visit date: Week 2, Week 4, Week 8, Week 12, Week 16 and Week 20.

Subgroup analyses for the primary endpoint will be performed to explore whether the treatment effect on the primary endpoint is consistent across subgroups. The influence of baseline and demographic characteristics on the treatment effect among participants will be explored via exploratory subset analyses for the following factors:

- Sex
- Age at diagnosis
- Race
- Region
- Background therapy
- Baseline disease severity and characteristics
- Dose level.

Treatment effects within each subgroup will be examined separately using the imputed data of the primary estimand and the model specified previously for the primary endpoint.

Forest plots will be generated displaying the estimated difference (the effect size of the primary treatment effect), 95% confidence intervals, and the corresponding p-value for each subgroup, with the overall result also included at the bottom. These subsidiary analyses are intended to provide reassurance that the observed treatment effect is consistent across all participant subgroups.

The study is not powered to detect differences between subgroups and any observed patterns should be interpreted extremely cautiously, owing to the smaller numbers and increased chance of type I error.

All listed subgroup analyses will be presented in a forest plot showing the effect size of the primary treatment effect in that subgroup.

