2.2 SAMPLE SIZE DETERMINATION

Determination of sample size is based on all globally enrolled participants. In this study, approximately 185 participants will be enrolled and randomized in a 1:1 ratio to each treatment group (satralizumab or placebo). Randomization will be stratified by baseline SOC treatment, region, and auto-antibody type as described in the Study Protocol, Section 3.1.

The estimated sample size required to demonstrate efficacy with regard to the MG-ADL is based on the AChR+ population and the following assumptions:

- The primary hypotheses test in the AChR+population is the difference between the placebo and satralizumab groups in the change from baseline to Week 24 in total MG-ADL score
- The assumed change from baseline to Week 24 in the placebo group is 2.3 points
- The assumed change from baseline to Week 24 in the satralizumab group is 4.3 points
- The assumed change from baseline accounts for approximately 10% of participants in the satralizumab group and approximately 20% of participants in the placebo group receiving rescue therapy
- The standard deviation (SD) of the change from baseline to Week 24 is 3.97 in both the placebo and satralizumab groups
- The assumed study treatment withdrawal rate is 10%

The assumptions are based on data reported in Howard et al. (2017). Due to changes in the treatment landscape the assumed mean change from baseline to Week 24 in the satralizumab arm is now assumed to be 4.3 (instead of 4).

Based on these assumptions and using a two-sided α level of 0.05, the sample size to achieve 85% power was estimated at 160 participants (80 per group) in the AChR+ population. Under the assumption that up to 25 participants meeting the study eligibility criteria will be AChR- (MuSK+ or LRP4+), the total study sample size will be approximately 185 participants. This sample size also provides approximately 80% power for an analysis of the difference between the placebo and satralizumab groups in the proportion of MG-ADL responders in the mITT and AChR+ population. This power calculation assumes a 50% response rate in the placebo group and a 75% response rate in the satralizumab group.

3. ANALYSIS SETS

The following populations are defined (Table 3):

Table 3 Analysis Sets

Population	Definition
Intent to treat (ITT)	All randomized participants. This excludes adolescents joining the study after the last adult participant is randomized.

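### The subgroup analyses ask whether the effect is consistent but plan no treatment-by-subgroup estimate, and the within-subgroup p-values do not address that question

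*SAP*

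**What the plan says.** SAP 4.2.5 gives the aim of the subgroup analyses as exploring whether the effect on the primary endpoint is consistent. It lists seven factors: sex, age at diagnosis, race, region, background therapy, baseline disease severity and characteristics, and dose level. Each subgroup is analysed separately, with the primary model on the primary estimand's imputed data. The forest plot carries the estimated difference, "95% confidence intervals, and the corresponding p-value for each subgroup", and the overall result at the bottom. The purpose is stated again: "These subsidiary analyses are intended to provide reassurance that the observed treatment effect is consistent across all participant subgroups".

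The plan limits these results in two places. SAP 4.2.4 makes p-values from sensitivity and supplementary analyses descriptive only. SAP 4.2.5 calls the subset analyses exploratory, says the study lacks power for differences between subgroups, and asks for great caution, citing small numbers and type I error.

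Neither SAP 4.2.5 nor Protocol 6.4.8, which lists the protocol's own subgroups, plans a treatment-by-subgroup term, estimate or test.

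**The concern.** Consistency is a statement about the difference in treatment effect between the levels of a factor. A within-subgroup p-value addresses another question: whether the effect in that level differs from zero. Its answer depends heavily on how many participants the level contains. If satralizumab has the same effect in everyone, smaller levels will often be non-significant through size alone.

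At stake is how the forest plot is read. A small level, such as participants above 100 kg under the dose-level factor, could be taken to lack benefit when the data say nothing of the kind. The SAP's caution names an increased chance of type I error. If the drug works, the likelier error in this display is the opposite one, non-significance from small numbers. The quantity that would answer the SAP's question, together with its uncertainty, is not displayed.

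**Working it through.** **Inputs from SAP 2.2**

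- Significance level: "using a two-sided α level of 0.05".
- Placebo change: "The assumed change from baseline to Week 24 in the placebo group is 2.3 points".
- Active change: "The assumed change from baseline to Week 24 in the satralizumab group is 4.3" points, so the difference is 4.3 − 2.3 = 2.0.
- SD: "The standard deviation (SD) of the change from baseline to Week 24 is 3.97 in both the placebo and satralizumab groups".
- Withdrawal: "The assumed study treatment withdrawal rate is 10"%.
- Size: "the sample size to achieve 85% power was estimated at 160 participants (80 per group) in the AChR+ population".

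**Reproducing the plan's figure.** n per arm = 2 × (1.96 + 1.036)² × 3.97² / 2.0² = 70.8, so 71. Dividing by 0.9 gives 79 per arm, 158 in total, against the stated 160. With 72 per arm (80 × 0.9), power = Φ(2/(3.97 × √(2/72)) − 1.96) = 85.6%. The SAP's figure is reproduced. The range used below is 72 to 80 per arm (N = 144 to 160).

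**Assumptions added here.** The documents give no subgroup sizes for this trial. A 50/50 split is assumed. A 70/30 split is also shown because Protocol 3.4.1 cites external real-world data suggesting that about 30% of patients may weigh more than 100 kg. The true effect is taken as 2.0 points in every level, and the SD as known.

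**Power within a level:** Φ(2/(3.97 × √(2/n)) − 1.96), with n per arm in that level.

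| Level | N = 160: n per arm | Power | N = 144: n per arm | Power |
|---|---|---|---|---|
| 50% | 40 | 61.5% | 36 | 57.0% |
| 70% | 56 | 76.0% | 50.4 | 71.5% |
| 30% | 24 | 41.5% | 21.6 | 38.0% |

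**Chance that one level is significant and the other is not:** p₁(1 − p₂) + p₂(1 − p₁).

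- 50/50, N = 160: 2 × 0.615 × 0.385 = 47%.
- 50/50, N = 144: 2 × 0.570 × 0.430 = 49%.
- 70/30, N = 160: 0.760 × 0.585 + 0.415 × 0.240 = 54%.
- 70/30, N = 144: 0.715 × 0.620 + 0.380 × 0.285 = 55%.

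The true difference between levels is zero in all four cases.

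**What the interaction estimate would give:** SE = 3.97 × √(2/n₁ + 2/n₂).

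- 50/50, N = 160: 3.97 × √(2/40 + 2/40) = 1.26; 95% CI half-width 2.46 points.
- 70/30, N = 160: 3.97 × √(2/56 + 2/24) = 1.37; half-width 2.68 points.

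At 50/50 and N = 160, power to detect a true 2-point difference between levels is 36%, and the difference detectable with 80% power is 3.5 points. Under a uniform effect, each factor's interaction interval excludes zero in 5% of trials.

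**The case against.** The strongest reply is that the plan does not rest on the p-values. Estimates and 95% CIs are plotted with the overall result, no significance rule is stated, the p-values are descriptive under SAP 4.2.4, and SAP 4.2.5 warns against over-reading. Comparing intervals with the overall result is a usable exploratory look at consistency. All of this stands, and it is why the point is minor.

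Three stronger readings are tempting, and the documents do not support them:

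- A reader might infer that consistency is judged by within-subgroup p-values. No such rule appears.
- A reader might infer that the plot is bound to look inconsistent. For one two-level factor, discordance by p-value is close to an even chance, and it matters only if the intervals are ignored.
- A reader might cite the chance that at least one of two equal levels is non-significant, 1 − 0.615² = 62% to 1 − 0.570² = 67.5%. That includes trials where both are non-significant (0.385² = 15% to 0.430² = 18%), and those levels do not disagree with each other.

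It is also fair to say that the interaction estimate is imprecise, that a reader could approximate it from the plotted estimates and intervals, and that each interval already shows whether its subgroup is significant. Reading seven interactions by significance would carry its own hazard: 1 − 0.95⁷ = 30% for at least one false signal if the factors were independent. These points argue for presenting an estimate with its interval rather than another p-value. They do not make the within-subgroup p-value relevant to consistency.

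**Conclusion.** The point holds as a mismatch between question and method in an exploratory, clearly caveated section. The SAP asks about consistency, plans no estimate of the difference between levels, and displays a p-value that does not bear on it. With a uniform effect at the SAP's own design values, one level is significant and the other is not in about 47% to 49% of trials at a 50/50 split, and 54% to 55% at 70/30. These figures rest on assumed splits, two-level factors and a known SD of 3.97. The primary test, its alpha, the testing hierarchy and the sample size are unaffected.

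**What to change.** In SAP 4.2.5:

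1. Remove the within-subgroup p-values. Keep the subgroup estimates and 95% CIs, with the overall result for reference.
2. For each factor, fit the primary ANCOVA on the imputed data with a treatment-by-subgroup interaction, using one term per non-reference level, and report the interaction estimate(s) with 95% CI. Take the variance from the jackknife described in SAP 4.2.3.5.
3. State that the interaction intervals will be wide, about ±2.5 points at a 50/50 split with N = 160, so they describe the uncertainty about consistency and cannot confirm it.

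The cost is a few extra model terms per factor and the matching jackknife runs, with no new data or imputation model. Factors with several levels, as race may have, need more than one term and will give wider intervals where levels are small.

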4.3 SECONDARY ENDPOINTS ANALYSES

Secondary endpoints are based on the following scores (see the Study Protocol for details):

- QMG: The QMG is a 13-item direct physician assessment scoring system that
 quantifies disease severity based on impairments of body functions and structures.
 Each item is quantitatively assessed and scored from 0 to 3 (where 3 represents the
 most severe), providing a total QMG score ranging from 0 to 39 (Clinical Review
 Report)
- MG-QoL: The MG-QOL-15 is a disease-specific health-related quality of life measure that consists of 15 items: mobility (9 items), symptoms (3 items), and contentment and emotional well-being (3 items). Items are scored on a Likert scale from 0 to 4 with the total score ranging from 0 to 60 (Burns et al. [2008])
- MGC: The MGC is a composite measure consisting of items drawn from the MG-ADL (chewing, swallowing, speech, and breathing), QMG (diplopia and ptosis), and Manual Muscle Test (hip, neck, facial, and deltoid strength) in an effort to include both clinician- and participant-reported elements in a single measure (Burns et al. [2008]). Each of the ten items contribute to a total score ranging from 0 to 50, with higher values indicating increasing symptom severity (Burns et al. [2010])
- Neuro-QoL: The Neuro-QoL Fatigue scale is a short form that is part of a collection of instruments and item banks, developed through a National Institute of Neurological Disorders and Stroke-sponsored initiative to evaluate the health-related quality of life of adults and children diagnosed with neurological disorders. It consists of eight items, each using a 5-level Likert scale ranging between 1=never to 5=always, with a 7-day recall period (Cella et al. [2012]).

4.3.1 Estimands for Secondary Endpoint Analyses

In addition to the primary estimand, the analysis of the secondary endpoints will rely on the responder estimand and the Duration Estimand. Except for the difference in estimands with regards to composite strategies, the analysis of secondary endpoints is the same as for the primary endpoint and will make use of the same imputation scheme.

4.3.1.1 ICE Strategies for Estimands for Secondary Endpoints

Endpoints depending on different estimands than the primary will still be computed on the imputed data set of the primary estimand and their ICE strategies will be implemented on top of the imputed data set:

- Responder Estimand: Same imputation as for primary estimand, if a participant requires rescue therapy the participant is categorized as non-responder (composite strategy). For example, for the secondary endpoint percentage of participants with a ≥2-point reduction from baseline in total MG-ADL score at Week 24, the dataset with MG-ADL score imputed as in Section 4.2.3.4. Completed MG-ADL will be used to identify the participants with a ≥2 point reduction from baseline. On top of that, if participants require rescue therapy the participant is categorized as non-responder
- Duration Estimand: Same imputation as for primary estimand, if a participant requires rescue therapy the participant will be imputed as not having an endured treatment effect after administration of rescue therapy (composite strategy).

The following table lists all secondary endpoints, the corresponding estimand, and relevance as secondary endpoint (Table 6). All populations are to be understood as the mITT restricted to the mentioned population. LRP4 & MuSK refers to the AChR- population.

Table 6 Secondary Endpoints and Corresponding Estimand and Relevance

Secondary Endpoint	Population	Relevance	Estimand Type (Generic)	
Mean change from baseline in MG-ADL score at Week 24	OP, LRP4 & MuSK	confirmatory	Primary (continuous) estimand: Difference in mean change of "Score" from baseline in "Population", treated with satralizumab vs placebo, in combination with	
Mean change from baseline in MG-ADL score at Week 24	MuSK	exploratory	stable background therapy, irrespective of taking rescue therapy, treatment discontinuation due to SDCR, as though participants with treatment discontinuation due to NSDCR continued treatment and as though participants	
Mean change from baseline in	AChR+, OP	confirmatory	with missing data after SDCR, rescue therapy, treatment interruption due to infection continued with placebo.	
QMG score at Week 24	LRP4 & MuSK	exploratory		
Mean change from baseline in	AChR+	confirmatory		
MG-QOL 15r total score at Week 24	OP	supportive		
WOOK 24	LRP4 & MuSK	exploratory		
Mean change from baseline in	AChR+	confirmatory		
MGC total score at Week 24	OP	supportive		
	LRP4 & MuSK	exploratory		
Mean change from baseline in	AChR+	confirmatory		
Neuro-QoL Fatigue Subscale total score at Week 24	OP	supportive		
total soore at Wook 24	LRP4 & MuSK	exploratory		
	AChR+, OP	supportive		

 Table 6
 Secondary Endpoints and Corresponding Estimand and Relevance

Secondary Endpoint	Population	Relevance	Estimand Type (Generic)
Percentage of participants with a ≥2-point (and more) reduction from baseline in total MG-ADL score at Week 24	LRP4 & MuSK	exploratory	reduction from baseline in Score at Week 24 between participants treated with satralizumab vs placebo, in combination with stable background therapy, as though participants with treatment discontinuation due to NSDCR continued treatment and as though participants with missing data after SDCR, treatment interruption due to infection continued with placebo as though participants receiving rescue therapy were not showing a reduction from baseline.
Percentage of participants with a	AChR+, OP	supportive	
≥3-point (and more) reduction from baseline in QMG score at Week 24	LRP4 & MuSK	exploratory	
Percentage of participants with a	AChR+, OP	supportive	
≥3-point (and more) reduction from baseline in total MGC score at Week 24	LRP4 & MuSK	exploratory	
Proportion of participants who	AChR+, OP	supportive	
have achieved minimal symptom expression (total MG-ADL score of 0 or 1) at Week 24	LRP4 & MuSK	exploratory	
Proportion of participants with at	AChR+, OP	supportive	
least one gMG related exacerbation between baseline and Week 24	LRP4 & MuSK	exploratory	

Duration (# consecutive	AChR+, OP		Duration Estimand: The difference in the mean duration of meaningful improvement at
visits) that participants show at least 2 point reduction from baseline MG-ADL	LRP4 & MuSK	exploratory	Week 24 in population between participants treated with satralizumab vs placebo, in combination with stable background therapy, as though participants with treatment discontinuation due to NSDCR continued treatment and as though participants with missing data after SDCR, treatment interruption due to infection continued with placebo as though
WIG-ADL			participants receiving rescue therapy were not showing a further reduction from baseline.

AChR = acetylcholine receptor; AChR+ = AChR-antibody seropositive (participants/population); gMG = generalized Myasthenia Gravis; LRP4 = low-density lipoprotein receptor-related protein 4; MG-ADL = Myasthenia Gravis Activities of Daily Living; ; MGC = Myasthenia Gravis Composite; MG-QoL = Myasthenia Gravis Quality of Life; MuSK = muscle-specific kinase; NSDCR = not study drug or condition related; OP = overall population; QMG = Quantitative Myasthenia Gravis score; QoL = quality of life; SDCR = study drug or condition related; Exacerbation = increase of non-ocular MG-ADL item by at least two points from baseline or achieving non-ocular item value of 3 when baseline was below 3.

4.3.2 Secondary Endpoints Under the Primary (Continuous) Estimand Framework

Secondary endpoints falling under the primary estimand framework (Table 6) will be analyzed the same way as the primary endpoint. The ANCOVA model will be analyzed by adjusting for the baseline value of the corresponding score, i.e., QMG change from baseline to 24 weeks will be adjusted for baseline QMG (instead of baseline MG-ADL).

The estimands for the secondary endpoints will be derived on the imputed data set of the primary estimand if the corresponding endpoint is solely based on the raw score.

4.3.3 Secondary Endpoints Under the Responder Estimand

To analyze secondary endpoints under the responder estimand framework (Table 6) each participant will have to be labelled as a responder or non-responder. This is done using the complete data set from the Imputation procedure and by applying the definition of the secondary endpoints. For a rationale on those responder definitions refer to the Study Protocol sections on MG-ADL, QMG and MGC responder definitions, which employ minimum clinically important difference derived in the relevant clinical literature. According to ICE specification of the responder estimand, participants that received rescue therapy will be imputed as non-responders (composite strategy) irrespective of the actual score in the completed data set.

A Cochran-Mantel-Haenszel test over the treatment groups stratifying for baseline stratification factors is the treatment effect estimator for the responder estimand. The estimate is the difference in proportion at Week 24.

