#### Intercurrent events:

- SDCR withdrawal from study treatment: treatment policy
- NSDCR withdrawal from study treatment: hypothetical
- Taking rescue therapy: composite (included in variable definition)
- Treatment interruption due to infection: treatment policy

Summary measure: The difference in the proportion of responders at Week 24

An estimate of the treatment effect will be computed using a Cochran-Mantel-Haenszel test adjusting for the randomization stratification factors (background therapy, autoantibody type, and region). Data following a NSDCR withdrawal from study treatment and any missing data will be imputed using multiple imputation as in the primary estimand.

Two endpoints require different considerations:

- The proportion of patients with at least one gMG related exacerbation
- The proportion of patients receiving rescue therapy between baseline and Week 24

In the first case, it is not possible to start a rescue therapy before observing a gMG related exacerbation. In the second, the event of interest is starting a rescue therapy. Therefore, starting a rescue therapy is not considered an intercurrent event for these endpoints and consequently is not included in the estimand definition.

Supplementary estimands will be detailed in the SAP and will include using a composite approach for the intercurrent event of SDCR withdrawal from study treatment.

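### The SAP files the exacerbation proportion under the responder estimand, whose rescue rule, read literally, counts rescued participants as free of exacerbation and conflicts with the protocol and with SAP Table 1

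*SAP*

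**What the plan says.** **SAP.** Section 4.3.1 states that, beyond the primary estimand, "the analysis of the secondary endpoints will rely on the responder estimand and the Duration Estimand". In Table 6 the row for participants with at "least one gMG related exacerbation between baseline and Week 24" follows the score-reduction and minimal-symptom rows and comes just before the Duration block. It is labelled supportive for AChR+ and the overall population. The opening words of the estimand cell for this block are incomplete in the text, but the row's position puts it in the responder group. The legible part of that cell says the analysis proceeds "as though participants receiving rescue therapy were not showing a reduction from baseline".

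Section 4.3.3 labels each participant from the completed data set "by applying the definition of the secondary endpoints", and then adds that "participants that received rescue therapy will be imputed as non-responders (composite strategy) irrespective of the actual score in the completed data set". The Table 6 footnote defines an exacerbation as an "increase of non-ocular MG-ADL item by at least two points from baseline or achieving non-ocular item value of 3" where baseline was below 3. The rescue endpoint has its own section (4.3.5); the exacerbation endpoint has none.

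**Protocol.** Section 6.4.4 lists the exacerbation and rescue proportions as two endpoints to be analysed outside the estimand framework. Section 6.4.5 gives the reason for the first: "it is not possible to start a rescue therapy before observing a gMG related exacerbation". It concludes that "starting a rescue therapy is not considered an intercurrent event for these endpoints".

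**The concern.** The responder rule was written for endpoints where meeting the definition is good. The exacerbation row counts participants who meet a bad definition. If the label is derived from the endpoint's own definition and rescued participants are then forced to not meeting it, the clearest cases of exacerbation enter the table as event-free. Planned rescue is twice as frequent on placebo, so the error would fall unequally on the arms and could shrink or even reverse the observed difference.

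The SAP states that it supersedes the protocol for regulatory filings, and its Appendix 1, which lists changes to the planned analyses, does not mention this endpoint. The protocol's exemption therefore does not protect it.

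A second problem is separate from rescue. The definition needs single MG-ADL items, while the completed data set that 4.3.1.1 and 4.3.3 tell the programmer to use is built from total scores.

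**Working it through.** **The plan's own figure.** The documents give no exacerbation rate, difference or power. The 20% and 10% rescue rates appear in the MG-ADL sizing (SAP 2.2, Protocol 6.1), with difference 4.3 − 2.3 = 2.0, SD 3.97, two-sided alpha 0.05, power 85% and 10% withdrawal.

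n per arm = 2 × (1.960 + 1.036)² × 3.97² / 2.0² = 70.75, so 71. Then 71 / 0.90 = 78.9, so 79 per arm and 158 in total, against the stated 160 (80 per arm). The figure reproduces.

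**How each source codes a rescued participant on this endpoint.**

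| Source | Consequence |
|---|---|
| SAP Table 6 placement with 4.3.3 | Non-responder whatever the score; literally, no exacerbation |
| SAP Table 1 | Rescue footnote is on the score-response, minimal-symptom and duration rows, not on this one |
| SAP 4.4.2.1 | Composite rescue rule covers the first four improvement endpoints, not time to exacerbation |
| Protocol 6.4.4 and 6.4.5 | Outside the estimand framework; rescue implies an earlier exacerbation |

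**Size under the literal coding.** Let r be the rescue rate (0.20 placebo, 0.10 satralizumab) and q the exacerbation rate among participants not rescued. q is not in the documents, so it is varied as an assumption.

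- Protocol reading: P = r + (1 − r)q.
- Literal SAP reading: P = (1 − r)q.
- Loss of arm difference = 0.20 − 0.10 = 0.10 for any q. At 80 per arm this is 0.20 × 80 = 16 against 0.10 × 80 = 8 participants.
- Share lost = 0.10 / (difference under the protocol reading).

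All differences are placebo minus satralizumab.

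| q placebo / satralizumab | Protocol reading | Difference (points) | Literal reading | Difference (points) | Share lost |
|---|---|---|---|---|---|
| 0% / 0% | 20.0% v 10.0% | 10.0 | 0% v 0% | 0.0 | 100% |
| 10% / 10% | 28.0% v 19.0% | 9.0 | 8.0% v 9.0% | −1.0 | 111% |
| 20% / 20% | 36.0% v 28.0% | 8.0 | 16.0% v 18.0% | −2.0 | 125% |
| 10% / 5% | 28.0% v 14.5% | 13.5 | 8.0% v 4.5% | 3.5 | 74% |
| 20% / 10% | 36.0% v 19.0% | 17.0 | 16.0% v 9.0% | 7.0 | 59% |
| 30% / 15% | 44.0% v 23.5% | 20.5 | 24.0% v 13.5% | 10.5 | 49% |
| 40% / 20% | 52.0% v 28.0% | 24.0 | 32.0% v 18.0% | 14.0 | 42% |
| 50% / 25% | 60.0% v 32.5% | 27.5 | 40.0% v 22.5% | 17.5 | 36% |

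The share exceeds one half only when the difference under the protocol reading is below 0.10 / 0.50 = 20 points.

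**What would make the loss smaller.** The 10 points assume every rescued participant would otherwise count as exacerbated, as Protocol 6.4.5 implies. If only 75% or 50% met the SAP item criterion, the loss would be 0.75 × 10 = 7.5 or 0.50 × 10 = 5 points. If rescue ran at half the planned rates (10% v 5%), the loss would be 5 points, or 8 against 4 participants.

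**The item definition.** SAP 4.2.3.4 fits one imputation model per efficacy score and fills in the change in that score. The partial-missingness rule in 4.2.3.2 also returns a prorated total. Neither step produces item values at a wholly missed visit, so the footnote criterion cannot be evaluated there.

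**The case against.** The strongest reply is that the SAP does not intend the harmful coding. Its Table 1 leaves the rescue footnote off this row, as Protocol Table 2 does. Section 4.3.3 refers for its rationale only to the MG-ADL, QMG and MGC responder definitions, and the legible Table 6 text speaks only of score reductions. Protocol 3.4.7.4 treats rescued patients as non-responders because rescue follows an exacerbation, so non-response is naturally the unfavourable outcome. On that reading a rescued participant counts as exacerbated and nothing is lost. This stands as a plausible reading. It does not settle the matter, because the SAP then supports opposite codes for the same participant and names neither.

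A second reply is that rescued participants would meet the item criterion anyway, since Protocol 3.1.5 asks for an MG-ADL before or immediately after rescue and the recall period is 7 days. That is likely for many, but not assured: 3.1.5 defines an exacerbation requiring rescue clinically, without an item threshold.

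A third reply is that counting rescue as an event overlaps with the confirmatory rescue endpoint. The overlap is real, but it follows from the protocol's own premise, and this endpoint is only supportive.

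A reader might go further and infer that most of the expected arm difference is erased, with a matching collapse in power. The documents do not support that. They state no expected difference or power for this endpoint, and the share lost depends on rates they do not give. The amendment rationale of SAP version 3 also reports few rescue administrations.

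**Conclusion.** The concern holds as a conflict in a stated rule. Placement in Table 6 together with the blanket rule in 4.3.3 leads, on a literal reading, to rescued participants being recorded without an exacerbation, against Protocol 6.4.4 and 6.4.5 and out of line with SAP Table 1. Separately, the event definition cannot be applied to the data set the SAP prescribes.

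The loss under literal coding is up to 10 percentage points. This rests on the planning rescue rates and on every rescued participant otherwise counting as exacerbated. The share of the total difference is undetermined: about 36% to over 100% in the range tried. The realised loss would be smaller if few rescues occurred, and nil if non-response is programmed as the unfavourable outcome. The endpoint is supportive and absent from the hierarchy in SAP 4.3.7, so neither type I error control nor any confirmatory test is affected. It should be corrected because a clinically important result could otherwise be diluted or reversed by a programming choice.

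**What to change.** Before unblinding, amend the SAP as follows:

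- Take the exacerbation row out of the responder estimand in Table 6 and exempt it from the rescue rule in 4.3.3.
- Derive the event from observed item-level MG-ADL at any double-blind assessment, including unscheduled visits.
- Count a participant rescued between baseline and Week 24 as having had an exacerbation, consistent with Protocol 6.4.5.
- State how participants with no further information are handled, as 4.3.5 does for rescue.
- Use the same Cochran-Mantel-Haenszel analysis as 4.3.5.

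The cost is one SAP paragraph and one table cell. No new data are needed, and the testing hierarchy does not change.
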